## 7. Trial treatment

The two arms of the trial are:-

- (1) Telephone friendship groups provided through the voluntary (charitable) sector
- (2) Usual health and social care.

Telephone friendship group intervention: This involves older people receiving befriending from their peers or from volunteers (who may also be older people) through phone calls which they receive in their own homes. Participants will be introduced to one-to-one telephone contact over a period of 6 short one-to-one calls with this being followed by facilitated telephone friendship groups. The support for telephone friendship groups is to be provided through study partners the Community Network. In this model older people are networked together through a teleconferencing system with assistance from an [service provider] volunteer facilitator. The Community Network has committed to providing training for facilitators and is able to host the teleconferences. The group of older people to be linked through teleconferencing may have a focus; for

example a book club or knitting group but this will not be necessarily the case. During the one-to-one calls the volunteers will introduce the concept of group discussions and explore preferences for the type of topics they might want to discuss in the groups. The Community Network will provide access to their telephone lines for weekly calls which will extend over a maximum of three months per recruitment cycle. The host charities will determine whether groups can continue after completion of the trial treatment with feasibility issues explored in the qualitative sub-studies (Section 10). Available evidence suggests that almost all older people have a landline telephone. There are potential issues regarding loss of hearing and the subsequent capacity of individuals to be able to use telephone friendship services effectively. We will screen for deafness in the initial interviews by observation at the screening visit and asking candidates about any equipment need. We will liaise with Action on Hearing Loss (formerly, Royal National Institute for the Deaf) to ensure that potential participants obtain appropriate assistive technology if they get randomised to receive the telephone friendship groups intervention. We will also ensure that any participant randomised to receive the intervention with sight loss, obtains assistance from the Royal National Institute for the Blind to enable them to take part.

Treatment as usual: Participants randomised to the control arm will not be receiving any study intervention. However they will participate in baseline and outcome measurement and the extent of their health and social care service usage will be assessed (as for all participants) by a health and social care resource use questionnaire designed for the study by the health economist. The resource use questionnaire will serve to check the comparability of services received by the control group across different study sites.

Management of co-morbidity: any unanticipated illness or risk situation that is observed in participant's and their homes at baseline or follow up will be managed in the following way:-

[figure not shown]
- a. In situations where accident, injury or other unforeseen occurrence is encountered the RA will alert the emergency services.
- b. In other non-emergency situations, the RA will report the observed problem to the Chief Investigator (GM) or their delegate (LG) who will take appropriate action (likely to involve encouraging the person to contact their GP).

Consent will be obtained from participants to share their information with The NHS Health and Social Care Information Centre and other central UK NHS bodies. This will alert the research team to a participant's health status and help to minimise the risk of telephoning or writing to participants who have died prior to follow-up.

Loss to follow up: A certain amount of attrition is inevitable during the period of intervention delivery which has been accounted for in the calculation of the target numbers for recruitment. Recruitment targets also anticipate a loss to follow up of 20%. Rigorous record keeping by the trials manager will ensure that loss to follow up will not occur due to administrative error.

## 8. Assessments and procedures

Figure 1 Participant flow

Procedures (and numbers provided in parenthesis) described below relate to the documentation outlined in Figure 1.

### Procedures required at first contact

A letter from **GP (1)** will be sent to community dwelling older people aged 75 and over. A **Response card (2)** will be included inviting the person to complete their contact details and return to the research team.

The research team will receive the completed **Response card (2)** and make contact with the candidate by telephone. The team will arrange for a suitable time for a RA to conduct a screening visit. During the initial telephone call the RA will inform the candidate that a **Participant Information Sheet (4)** will be sent to their home address which provides information about the study and that they may want to read it in advance of the visit. On request, the RA will send the Participant Information Sheet via email.

The research team will make concerted efforts to make first contact with those who express an interest in participating from the information received on the **Response card (2)**. At least three telephone messages will be left and a minimum of six calls will be made to candidates where there is no facility to leave a message. If the candidate has provided an email address, the research team will also attempt to make contact via this method; including, where no telephone number has been provided on the response card. Reasons for non-contact will be recorded and may include:

- Still trying to contact
- No usable contact information
- Language requests other than English
- No facility to leave messages (min 6 calls attempted)
- Left 3 or more messages, no further follow-up.

Due to the nature of the study population, supplementary recruitment methods will also be employed to initiate first contact (see Figure 2). Third sector and other partner organisations will be given study information to enable them to discuss the study with candidates. Other 'referrers' may also be District Nurses, Occupational Therapists or other (allied) health or social care professionals. Additionally, **study promotion text (6)** displayed on posters, leaflets or adverts will be distributed by partner organisations to individuals who may be interested in finding out more about the study. Candidates will be given contact details for the research team so they can make first contact. The research team will receive enquires and record the same information about the candidate on the **First Contact form (2a)** which records the same information as the **Response card (2)**. This will enable a screening visit to be arranged in the same way as with other recruitment strategies. The method of referral and attempts made to contact the candidate will be recorded in order to inform the feasibility assessment (see Section 3). The **First Contact form (2a)** will also record why eligible candidates chose not to take part (the option not to specify a reason will be offered).

[figure not shown]
Further to this, members of the South Yorkshire Cohort (SYC) may be used to identify candidates, subject to approval by Leeds REC which oversees the SYC.

### Recruitment strategies

Figure 2 Describes recruitment strategies used in the study.

### Figure 2. Methods of recruitment

The Participant Information Sheet will be sent to potential participants at their home (or via email, if requested), immediately after first telephone contact, which will usually be 5 days prior to the screening visit, to allow time for their consideration (see Figure 1 above).

#### Procedures required at screening visit

A RA will visit the potential participant at home and will read through the **Participant Information Sheet (4)**, answer questions and administer:

- **Six Cognitive Impairment Test (5)**
- **Screening Checklist (6)**

The research team will record reasons of ineligibility and for non-participation will be invited (with the option to not specify) using the **Screening Checklist (6)**. These documents (5 and 6) are combined within the **Eligibility form** (submitted to REC). Recording reasons of ineligibility will aid the recruitment strategy as the trial progresses. Basic details (age, sex, reason for exclusion/non-participation) will be collected to allow completion of the revised CONSORT diagram (Schultz et al, 2010) – see appendix 1.

If a candidate is found not eligible, following a score of 8 or more on the **6CIT (5)** the following procedure will apply. The RA will thank the individual and inform them that a member of the research team will be in touch shortly. The Chief Investigator (GM) or their delegate (LG) will make direct contact with the candidate to discuss the 6CIT score and encourage the person to contact their GP.

If the candidate cannot be contacted within approximately one week of the original eligibility interview, a **6CIT non-eligible candidate letter** will be sent to the candidate. This will include an explanation of why it is not appropriate for them to participate in the study; and, advise that they should take the letter (which will include their score) to their GP. The letter will also include contact details should they wish to discuss the content of the letter further. The reason for non-eligibility will be recorded.

#### Procedures required before randomisation

A member of the research team will meet and consent the candidate at home **Participant Consent Form (7)**. Candidates will be offered as much time as they need to consider their decision however; consent will be permitted at the screening visit if requested by the candidate. Participants will be randomised by the research team. This will be recorded on the **Consent and Randomisation sheet (7a)** which will also capture reasons for non-consent. At this point the research team will capture information about any assistance required to participate in the study e.g. sight/ hearing loss or manual dexterity.

Baseline measurement will be administered face-to-face following consent and before randomisation by the research team and includes:

- **SF-36 plus ONS wellbeing and telephone service cost questions (8)**
- **Patient Health Questionnaire (PHQ-9) (9)**
- **EQ-5D (10)**
- **General Self Efficacy Scale– GSE (11)**
- **de Jong Loneliness Scale (12)**
- **Health and Social Care Resource Use Questionnaire(13)**
- **Socio-demographics (14)**

#### **Procedures required after randomisation (Intervention arm only)**

Participants randomised to receive the research intervention will be sent **Telephone Friendship Group Questions & Answers** by post; or, via email upon requested). The information will answer some of the practical questions participants may have about how they will receive calls and what to expect.

#### **Study reminder (2 and 4 months)**

All participants will receive a **Contact card (17)** by post from the research team, at 2 and 4 months. The brief card will thank the participant, provide an update on progress and a reminder that we will be in touch again in another 2 months.

#### **Procedures required at six month follow-up**

Six month follow-up data will be collected by the Research Assistant (RA) via telephone. Follow up data will involve completion of the following;

- **SF-36 plus ONS wellbeing and telephone service cost questions (8)**
- **PHQ-9 (9)**
- **EQ-5D (10)**
- **GSE (11)**
- **de Jong Loneliness Scale (12)**
- **Health and Social Care Resource Use Questionnaire (13)**
- **SAE Checklist (17)**

We anticipate that 20% of participants will require assistance face-to-face. In these cases the RA will seek permission to visit the participant at home to administer the questionnaire (**essential documents 8-13 and 17**) face-to-face. Approximately 4 (5%) telephone calls (in each recruitment wave) will be recorded, with consent, for researcher training and monitoring purposes.

Some participants in the intervention arm will be invited to participate in a **semi-structured interview (16)** as part of the qualitative sub-study (see Section 10 below). An RA will ask permission to either visit the participants' home, or to telephone them to conduct the interview.

### **Study reminder (8 and 10 months)**

All participants will receive a **Contact card (17)** by post from the research team, at 8 and 10 months. The brief card will thank the participant, provide an update on progress and a reminder that we will be in touch again in another 2 months.

### **Procedures required at twelve month follow-up**

Twelve month follow-up data will be collected by the Research Assistant (RA) via telephone. Follow up data will involve completion of the following;

- **SF-36 plus ONS wellbeing and telephone service cost questions (8)**
- **PHQ-9 (9)**
- **EQ-5D (10)**
- **GSE (11)**
- **de Jong Loneliness Scale (12)**
- **Health and Social Care Resource Use Questionnaire (13)**
- **SAE Checklist (17)**

We anticipate that 20% of participants will require assistance face-to-face. In these cases the RA will seek permission to visit the participant at home to administer the questionnaire (**essential documents 8-13 and 17**) face-to-face. Approximately 4 (5%) telephone calls (in each recruitment wave) will be recorded, with consent, for researcher training and monitoring purposes.

### **Procedures for withdrawal from the trial treatment or from the study**

The participant will inform the research team (or the facilitator of the group) if they want to discontinue with the telephone friendship intervention. Follow-up will continue unless the participant explicitly withdraws their consent for follow-up. Data collected up to this point will be included and anonymised.

The research team will record reasons for withdrawal from the study where possible. The participant will be informed that they do not have to give a reason.

### **Procedures for attempted follow-up of participants “lost to follow-up”**

Participants will be considered lost-to-follow-up if they fail to respond to three telephone messages and one reminder letter. A minimum of six calls will be made to candidates where there is no facility to leave a message. If the candidate has provided an email address, the research team will also attempt to make contact via this method. For those participants previously identified (at earlier points in the study) as requiring assistance, an additional telephone call will be made. There are no procedures for further follow-up.

### **Procedures required when closing a trial (premature or planned).**

At the point at which all questionnaires have been collected (or participants have failed to respond despite reminders) and all data have been entered and cleaned, the management group will approve closure of the database. Further details will be presented in the **data management and monitoring plan** (not submitted to REC).

### **Procedures required to record (serious) adverse events**

In line with previous studies which deliver interventions to promote self-efficacy, we do not anticipate adverse events associated with the research interventions. Four categories of serious adverse events (SAEs) will be recorded during follow-up: results in death; is life-threatening; requires hospitalisation (initial or prolonged); results in persistent or significant disability or incapacity. The collection and reporting of SAE data will be governed by Sheffield CTRU standard operating procedures.

At each follow-up (as described above), participants will be asked if they have experienced any event or illness in the last six months which:

- has required unscheduled hospitalisation; or,
- has resulted in persistent or significant disability / incapacity (see appendix 2).

Information obtained from the NHS Health and Social Care Information Centre will be used to inform the collection and reporting of SAEs, where appropriate.

*It is the Chief Investigator's responsibility:*

1. To follow the procedure outlined in the study protocol for the reporting of SAEs;
2. To assess each event for causality and AE category;
3. To provide the Dean of SchARR and the University Research Office (in their capacity as representatives of the sponsor) with details of all SAEs identified within agreed timeframes;
4. To notify the Trial Steering Committee and Data Monitoring and Ethics Committee of any SAEs where appropriate; and,
5. To submit the annual safety report to the REC.

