intervention will be presented to the Trial Steering Committee for their independent view of what might be controlled and/or eliminated for the purposes of the trial. We will also convene a Local Implementation Group (LIG), to meet bi-monthly for the duration of the recruitment and implementation phase to ensure that methods of recruitment and delivery match the local context and that the intervention remains acceptable for longer term roll-out in practice. The LIG will include a local older person as a lay representative and appropriate personnel from Age UK, NHS and LA.

The intervention does present some risks to the participant. The intervention may bring up painful memories. To mitigate this risk [service provider] volunteer facilitators will be trained, and give guidance, on choosing topics for discussion. One-to-one calls will explore topic choices with individual participants before group discussions commence. The volunteers will receive specialised training to monitor conversations and pick up on any distress. All participants will be contacted by the research team at baseline, six month and twelve month follow-up. In addition, we intend to contact all participants at regular intervals (see section 8) to maintain contact and help participants feel involved throughout. Participants in the intervention arm will experience more contact.

The participant may experience transient dissatisfaction. Group interventions have occasional found participants experience a level of transient dissatisfaction with the intervention. To mitigate this risk volunteer facilitators will receive training to enable them to deal with situations which may arise e.g. a participant experiencing some boredom due to the choice of topic chosen by the group. The benefits to the participant may include: tolerance of others and listening skills.

Participants in the telephone friendship groups may want to continue to have discussions over the telephone after the twelve week period has ended. In this situation, the [service provider] volunteer will discuss this with the group. It will be for the service providers to decide if they can support the groups to continue in the same way. Issues relating to sustainability of groups will also be explored in the ancillary sub-studies (see Section 10).

This trial will be conducted in compliance with the protocol, GCP and the NHS research governance framework.

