### Statistical criteria to terminate the trial

There are no statistical criteria for stopping the trial early; as the intervention is considered low risk. Decisions to stop the trial early on grounds of safety or futility will be made by the Trial Steering Committee or funding body on the basis of advice from the DMEC.

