Appendix 1: Revised CONSORT 2010 Flow Diagram

Appendix 2: Serious Adverse Event Checklist (6 month and 12 month follow-up)

DETAILS:

\* If details are unclear was permission granted to contact GP for verification and/or confirmation?

Yes  No

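### Call-linked distress is a named risk, but only serious adverse events are recorded, so non-serious distress has no stated count and no stated route to the DMEC

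*Protocol*

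**What the plan says.** - **The risk.** Protocol Section 1, Risks and Benefits, states: "The intervention does present some risks to the participant. The intervention may bring up painful memories". The mitigations are guidance on topics, exploring topic choices one-to-one before groups start, and training: "The volunteers will receive specialised training to monitor conversations and pick up on any distress". Issues that emerge through delivery "will be presented to the Trial Steering Committee for their independent view".
- **Event recording.** Protocol Section 8, Procedures required to record (serious) adverse events, states: "we do not anticipate adverse events associated with the research interventions. Four categories of serious adverse events (SAEs) will be recorded during follow-up". The four categories are death, threat to life, hospitalisation, and lasting or significant disability. The two follow-up questions ask about unscheduled hospital stays and lasting disability. The reference to unit procedures is to SAE data.
- **Notification.** In the same section one of the Chief Investigator's duties is "To notify the Trial Steering Committee and Data Monitoring and Ethics Committee of any SAEs where appropriate". The event form listed at six and twelve months, and shown in Appendix 2, is an SAE checklist.
- **Stopping.** Section 9 sets no statistical stopping criteria, "as the intervention is considered low risk". Stopping for safety is decided by the TSC or the funder on DMEC advice.
- **Withdrawal.** The Section 8 heading "Procedures for withdrawal from the trial treatment or from the study" covers both kinds of withdrawal, but the sentence on recording reasons refers only to leaving the study.
- **Registers.** Section 10.2 has facilitators complete an attendance register at every one-to-one and group session.

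**The concern.** One section foresees a psychological harm specific to the calls and trains people to detect it. The section that decides what is recorded starts from the expectation that the intervention will cause no adverse events, and it provides for SAEs alone. A volunteer who notices distress has no stated place to record it as an event.

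Two things are at stake. The DMEC advises on stopping for safety without a stated count of the psychological harm that the protocol itself foresees. And the final report could not say how many intervention participants were affected. Nothing in the efficacy analysis depends on this.

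**Working it through.** The plan gives no figure to reproduce here. The check has two parts: whether any other provision supplies the count or the DMEC route, and what recording would involve.

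**Other provisions**

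- *Delivery issues* (Section 1, Risks and Benefits) go to the TSC, not the DMEC, and are not stated to be participant-level counts.
- *Facilitator diary* (Section 10.2) records difficulties in delivering the intervention, for the fidelity assessment.
- *Problems seen by the research assistant* (Section 7) are those observed in participants and their homes at baseline or follow-up, not during calls.
- *Concern procedure for interviews* (Section 10.3) covers the qualitative interviews.
- *Chief Investigator's duty to classify events* (Section 8) mentions adverse event category, but no step for collecting non-serious events precedes it.
- *SF-36 Mental Health and PHQ-9* at 6 and 12 months may show lasting effects by arm. They do not count call-linked episodes, and by Section 2 the six-month assessment comes when the calls are finished or well underway.

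None of these is stated to count non-serious distress linked to a call or to send it to the DMEC.

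**Recording load at full attendance**

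Inputs: 124 randomised to the intervention (Section 9); 12 weekly group sessions and up to 6 one-to-one calls each (Sections 1 and 7); about 24 volunteers retained (Section 1).

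- Group entries: 124 × 12 = 1,488
- One-to-one entries: 124 × 6 = 744 at most
- Total: 1,488 + 744 = 2,232 at most
- Per retained volunteer, if spread evenly: 2,232 / 24 = 93

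The entry has to be made per participant. One tick per group session could not show which of about six people was distressed, so it could not support a percentage of participants.

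**DMEC meetings while calls run**

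Inputs: recruitment starts in month 8, intervention delivery in month 11, and recruitment is complete in month 20 (Trial Summary, Project Timetable); wait of 0 to 2 months and intervention of 4 to 5 months (Section 2); DMEC every 6 months from the start of recruitment (Section 11).

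- Earliest end of calls for the last participant: 20 + 0 + 4 = month 24
- Latest end: 20 + 2 + 5 = month 27
- DMEC meetings: 8 + 6 = 14, then 20, 26 and 32

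Months 14 and 20 fall within delivery in every case. Month 26 does so only towards the longer end of the wait and duration. The count could therefore reach the DMEC at two or three meetings during delivery.

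**The case against.** The strongest case against is that nothing here is an error. A reader might infer that the two sections flatly contradict each other. They do not: one says the intervention may bring up painful memories and lists mitigations, the other says adverse events are not expected, and a mitigated possibility can stand beside that expectation. The protocol never calls momentary upset an adverse event. The sections are in tension, no more.

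A reader might also infer that distress is invisible to oversight. The documents do not support that either. Delivery issues reach the TSC, which with the funder decides on stopping. Diaries and interviews may describe cases, and non-adherent participants are to be asked why the intervention did not suit them. SF-36 Mental Health and PHQ-9 give a randomised comparison of lasting psychological state, which a one-arm tick cannot.

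The register and diary forms, the unit's procedures and the data management plan are not shown, and Appendix 2 survives only in part. Any of them might hold a suitable field.

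What stands is narrower. The protocol as written states neither a count of non-serious call-linked distress nor a route for it to the DMEC, and the other provisions are not stated to supply either.

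**Conclusion.** The point holds as a minor, inexpensive improvement to safety recording. As written, the trial could not report how often the psychological harm it foresees occurred below the SAE threshold, and the DMEC would have no stated count of it.

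It should not be read as a claim that SAE-only recording is improper; for an intervention considered low risk that is a defensible choice. The weakness is that the choice rests on a statement of expectation that sits badly with the risk section. No rate of distress is given or assumed. Sample size and the primary comparison are unaffected.

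The conclusion rests on what the protocol states, since the relevant forms are not shown. The load of 2,232 entries assumes full attendance and all six one-to-one calls, so it is an upper figure. The two to three meetings assume the stated timetable is kept.

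**What to change.** 1. In Section 8, Procedures required to record (serious) adverse events, replace the statement that no intervention-related events are expected. Say that calls may cause distress, and that call-linked distress below the SAE threshold will be recorded in the intervention arm. Distress that meets an SAE category still follows the SAE route.
2. Add a yes/no distress prompt for each participant to the existing attendance register (Section 10.2). Give it a tight definition, for example: *the participant said the call upset them, or the call was paused, ended or followed up because of distress*.
3. In the Section 8 withdrawal procedures, state that the reason for stopping the calls is recorded where the participant is willing to give it.
4. Have the trial manager, who is not blinded (Section 3), compile the entries. During the trial, send the arm-level count to the DMEC. Individual delivery issues still go to the TSC, without arm-level totals, so that its blinding is kept.
5. At the end, report descriptively the number and percentage with recorded distress out of all those randomised to the intervention.

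The cost is protocol wording, one register prompt (up to about 2,232 ticks, about 93 per retained volunteer), one reason field, brief guidance within the existing facilitator training, and the trial manager's time to compile the entries. No new visit or committee is needed. The downsides are that the count exists in the intervention arm only, relies on volunteers' judgement, will probably miss cases and allows no between-arm test.

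### The serious adverse event categories to be recorded do not match what participants are asked: no prompt or source is specific to life-threatening events, and hospitalisation is prompted more narrowly than it is defined

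*Protocol*

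**What the plan says.** Under *Procedures required to record (serious) adverse events* (Protocol, Section 8), the plan commits to this: "Four categories of serious adverse events (SAEs) will be recorded during follow-up: results in death; is life-threatening; requires hospitalisation (initial or prolonged"). The fourth category is an event that "results in persistent or significant disability or incapacity".

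The next paragraph describes how events are found. At each follow-up "participants will be asked if they have experienced any event or illness in the last six months which" meets one of two conditions: it "has required unscheduled hospitalisation; or" it "has resulted in persistent or significant disability / incapacity". The second condition points to the checklist in Appendix 2. The checklist is listed among the documents for the six- and twelve-month follow-ups.

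A further source is then named: "Information obtained from the NHS Health and Social Care Information Centre will be used to inform the collection and reporting of SAEs, where appropriate". Section 7 describes what this information offers: "This will alert the research team to a participant's health status". It adds that the information helps the team avoid contacting participants who have died.

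The Chief Investigator assesses each event for causality and category and sends an annual safety report to the ethics committee. Collection and reporting are placed under the trials unit's standard operating procedures, which are not part of the document.

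**The concern.** The list of what will be recorded and the list of what will be asked stand in adjacent paragraphs and do not agree. Life-threatening events are a recorded category, but no prompt asks about them. Hospitalisation is a recorded category covering initial and prolonged stays, but the prompt is confined to unscheduled admissions.

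What is at stake is the meaning of the safety counts. Section 9 gives no statistical stopping criteria, so a decision to stop on safety grounds rests on the data monitoring committee's advice. That committee and the ethics committee need to know whether a hospitalisation count covers all admissions or only unscheduled ones. They also need to know whether a low count of life-threatening events means that few occurred or that the question was not put.

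**Working it through.** No sample size, power or event figure enters this point, so there is nothing to recompute. The check sets each recorded category against the participant prompts and the other sources the protocol states.

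1. **Death.** No participant prompt is possible. Information from the NHS Health and Social Care Information Centre serves instead (Sections 7 and 8). Covered.
2. **Life-threatening.** No prompt is listed, and no source names it. There are two indirect routes. If the event also caused an unscheduled admission or lasting disability, it is prompted for under that heading and can then be categorised as life-threatening. Otherwise it may come to light through the NHS information, which the protocol ties to no particular category and uses only where appropriate. An event with no unscheduled admission, lasting disability or death depends on that second route alone.
3. **Hospitalisation, initial or prolonged.** Prompted, but only when unscheduled. That qualifier appears in the prompt and not in the category, and no exclusion of planned admissions is stated. Prolongation of an unscheduled stay falls inside an admission already asked about. A scheduled admission for a new illness, or a planned stay prolonged by a complication, can meet the category as worded but is not asked about.
4. **Lasting disability or incapacity.** The prompt matches the category.

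Of the four categories, one is prompted as defined (disability), one is prompted more narrowly (hospitalisation) and two have no prompt (death and life-threatening): 1 + 1 + 2 = 4. Of the two without a prompt, death has another clearly stated source. Life-threatening events have only the general one.

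Other contacts do not close the difference. The cards sent at 2, 4, 8 and 10 months thank the participant, report progress and give a reminder; no event question is described. The Chief Investigator's assessment can classify only events that have already been identified.

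**The case against.** The strongest reply is that the prompts are a screen and not the classification. Participants, mostly by telephone, are asked about consequences they can recognise, and the Chief Investigator then assigns the category. The visible part of Appendix 2 asks whether permission was given to contact the GP when details are unclear. On this reading most life-threatening events arrive through the admission question, with NHS information behind it. This stands. A reader might infer that life-threatening events have no route into the data at all, or that the category must come out nearly empty. The documents do not support either inference.

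Second, nearly all of the Appendix 2 form is missing from the text available, and the operating procedures are not shown. This also stands as far as it goes: the form is evidence neither way, and it cannot be said that it lacks a life-threatening item. But the section's own text gives two conditions joined by *or*, and that list differs from the categories printed just above it. An unseen form or procedure does not make the two printed lists agree.

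Third, asking about unscheduled admissions is a sensible way to separate events from elective care, since a planned admission is not in itself an adverse event. That may well be the intention. If so, the recorded category should say so, and it does not.

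Finally, the protocol regards the intervention as low risk and anticipates no adverse events associated with it. That bears on how much this matters, not on whether the lists agree.

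**Conclusion.** The inconsistency is real but minor. As written, the protocol says it records four categories while its stated prompts cover one as defined and a second in narrower form, and nothing specific to life-threatening events is named. Followed literally, the counts would not correspond to the stated definition in a few situations: a scheduled admission for a new illness, a planned stay that is prolonged, or a life-threatening event without an unscheduled admission or lasting disability.

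How many events this involves cannot be worked out from the documents. It is probably small among the 248 participants planned, on the assumption that many life-threatening events lead to an unscheduled admission. The conclusion also takes the two conditions in the text as the full list of prompts; if the Appendix 2 checklist already has a life-threatening item, what remains is the hospitalisation wording and an incomplete description in the section. This is a point of safety ascertainment only and does not touch sample size, power, the primary outcome or its analysis.

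**What to change.** Reconcile the two lists in the adverse event procedures so that the safety table and the annual report count exactly what is ascertained. Either of two routes would do:

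- Extend the six- and twelve-month prompts to match the recorded categories. This means adding a life-threatening item if the Appendix 2 checklist does not already contain one, and aligning the hospitalisation wording.
- Restate the recorded categories to match the prompts, say explicitly whether planned admissions are excluded, and name the source for each category, including what the NHS information is relied on to supply.

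The cost is a wording edit and at most one extra checklist line per follow-up.
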